12.5.1.2 Change in spleen volume and spleen length

Spleen volume will be measured by MRI/CT at baseline, the end of Cycle 8 (NIS793 arms) or Cycle 6 (all other arms), the end of Cycle 16 (NIS793 arms) or Cycle 12 (all other arms) and at EOT (if not performed in the past 12 weeks) as noted in Table 8-6. The change from baseline will be summarized at each scheduled assessment time point during the core treatment phase using descriptive statistics.

The proportion of subjects with a spleen volume progression from baseline to the end of Cycle 8 (NIS793 arms) or Cycle 6 (all other arms) and the end of Cycle 16 (NIS793 arms) or Cycle 12 (all other arms) during the core treatment phase will be summarized descriptively. A spleen progression requires confirmation by MRI or CT showing a spleen volume increase of at least 25%.

The proportion of subjects achieving at least 25% and 35% reduction in spleen volume from Baseline to the end of Cycle 8 (NIS793 arms) or Cycle 6 (all other arms) and the end of Cycle 16 (NIS793 arms) or Cycle 12 (all other arms) during the core treatment phase as measured by MRI or by CT will be summarized descriptively.

Spleen length measurement will be conducted by manual palpation. Manual palpation will be performed on days 1 and 15 of cycles 1 to 3, and day 1 of subsequent cycles, as noted in the schedule of assessments in Table 8-3 and Table 8-5. The change from baseline at each planned scheduled point during the core treatment phase will be summarized using descriptive statistics.

The proportion of subjects who achieved at least 50% spleen length reduction at the end of Cycle 8 (NIS793 arms) or Cycle 6 (all other arms) from baseline during the core treatment phase for subjects with baseline splenomegaly that is palpable at greater than 10 cm, or became not palpable for subjects with baseline splenomegaly that is palpable at $\geq 5-\leq 10$ cm will be estimated.

The proportion of subjects who achieved at least 50% spleen length reduction at the end of Cycle 4 (NIS793 arms) or Cycle 3 (all other arms) from baseline during the core treatment phase for subjects with baseline splenomegaly that is palpable at greater than 10 cm, or became not palpable for subjects with baseline splenomegaly that is palpable at $\geq 5-\leq 10$ cm will be estimated.

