Pooling of center: Unless specified otherwise, data from all study centers will be pooled for the analysis. Due to expected small size of centers, no center effect will be assessed.

Qualitative data (e.g., gender, race, etc.) will be summarized by means of contingency tables by treatment group; a missing category will be included as applicable. Percentages will be calculated using the number of subjects in the relevant population or subgroup as the denominator.

Quantitative data (e.g., age, body weight, etc.) will be summarized by appropriate descriptive statistics (i.e. mean, standard deviation, median, minimum, and maximum) by treatment group.

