Safety summaries (tables, figures) include data from the pre-treatment period (to display the baseline status e.g. for ECG) and the on-treatment period, i.e. data from the post-treatment period with the exception of deaths should not be included unless requested from Health Authorities or external committees.

In particular, summary tables for adverse events (AEs) will summarize on-treatment events, with a start date during the on-treatment period, the so-called ***treatment-emergent*** AEs. Additionally, all (study treatment related/ regardless) AEs and SAEs with a start date during the overall safety period will be summarized.

However, all safety data (including those from the post-treatment period) will be listed and those collected during the pre-treatment, post-treatment overall safety period and post-treatment period are to be flagged.

For the final analysis, all extension treatment phase safety data will be listed and those collected during post-treatment overall safety period and post-treatment period are to be flagged. The safety data in part 1 core and extension phase will be summarized in tables for the extension treatment phase clinical trial safety disclosure.

Windows for multiple assessments

In order to summarize data collected over time (including unscheduled visits), the assessments will be time slotted. The following general rule will be applied in creating the assessment windows: If more than one assessment is done within the same time window, the assessment performed closest to the target date will be used. If two assessments within a time window are equidistant from the target date, then the assessment that occurred later will be used. If multiple assessments occur on the same date then the worst case will be used. Data from all assessments (scheduled and unscheduled), including multiple assessments, will be listed.

The following time windows are defined for descriptive summary on spleen imaging, spleen length palpation, ePROs, laboratory assessments [REDACTED] (Tables 2-1, 2-2, and 2-3) by visit regardless of core or extension treatment phases. The end of treatment assessment will be mapped into the time points as needed.

Table 2-1 Time windows for imaging assessments (MRI/CT of abdomen)

Time Point	Planned Visit Timing	Time Window Definition
Screening/Baseline	On or before Study Day 1*	≤ Study Day 1
Cycle 7 Day 1	Study Day 168	Study Days 140 – 196
Cycle 13 Day 1	Study Day 336	Study Days 308 – 364
Every 6 cycles thereafter		

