Cycle $y=13+6*k$ Day 1 (with $k = 1, 2, \dots$)	Study Day $(13+6*k-1)*28$	Study Days $(13+6*k-1)*28-28$ to $(13+6*k-1)*28+28$

* Study Day 1 = Date of first administration of study treatment (start of study treatment)

EOT core and EOT extension assessments are mapped to the corresponding time points based on the defined time window.

Table 2-2 Time windows for ePROs, laboratory assessments (chemistry, coagulation, urinalysis and thyroid function) [REDACTED]

Time Point	Planned Visit Timing	Time Window Definition
Baseline (Cycle 1 Day 1)	On or before Study Day 1*	≤ Study Day 1
Cycle 2 Day 1	Study Day 29	Study Days 15 – 42
Cycle 3 Day 1	Study Day 57	Study Days 43 – 70
Cycle 4 Day 1	Study Day 85	Study Days 71 – 98

Cycle 5 Day 1	Study Day 113	Study Days 99 – 126
Cycle 6 Day 1	Study Day 141	Study Days 127 – 154
Cycle 6+k Day 1 (with k = 1, 2, ...)	Study Day (6+k-1)*28+1	Study Day (6+k-1)*28+1-14 to (6+k-1)*28+14
Post treatment		
30-day safety follow-up	Post treatment study day 30	Post treatment study days 23 – 37
90-day safety follow-up	Post treatment study day 90	Post treatment study days 83 – 97
105-day safety follow-up	Post treatment study day 105	Post treatment study days 98 – 112
150-day safety follow-up	Post treatment study day 150	Post treatment study days 136 – 164

* Study Day 1 = Date of first administration of study treatment (start of study treatment)
 EOT core and EOT extension assessments are mapped to the corresponding time points based on the defined time window.
 Post treatment study day 1 = end of study treatment date + 1
 Post treatment visits are for laboratory chemistry assessments only
 90-day safety follow-up visit for NIS7393 arm(s)
 90-day safety follow-up visit, and 150-day safety follow up visit are for sabatolimab arm(s)
 105-day safety follow-up visit is for crizanlizumab arm(s)

Table 2-3 Time windows for spleen length palpation assessments and hematology laboratory assessments

Time Point	Planned Visit Timing	Time Window Definition
Baseline (Cycle 1 Day 1)	On or before Study Day 1*	≤ Study Day 1
Cycle 1 Day 15	Study Day 15	Study Days 8 – 21
Cycle 2 Day 1	Study Day 29	Study Days 22 – 35
Cycle 2 Day 15	Study Day 43	Study Days 36 – 49
Cycle 3 Day 1	Study Day 57	Study Days 50 – 63
Cycle 3 Day 15	Study Day 71	Study Days 64 – 77
Cycle 4 Day 1	Study Day 85	Study Days 78 – 98
Cycle 5 Day 1	Study Day 113	Study Days 99 – 126
Cycle 6 Day 1	Study Day 141	Study Days 127 – 154

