2.7.1 Secondary endpoints

All secondary efficacy endpoints will be analyzed using the Full Analysis Set (FAS).

Proportion of subjects achieving improvement of hemoglobin level (NOT applicable)

Hemoglobin is measured at baseline and at least once per cycle. The change from baseline will be summarized by treatment group using descriptive statistics. Individual hemoglobin level at different time points will be displayed graphically by treatment group.

The proportion of subjects achieving improvement in hemoglobin ≥ 1.5 g/dL and ≥ 2.0 g/dL, respectively, from baseline to the end of Week 24, and the end of Week 48 will be summarized using descriptive statistics (N, %) by treatment arm along with two-sided exact binomial 95% CIs [[Clopper and Pearson 1934](#)]. The proportion will be calculated using FAS subjects as the denominator; the numerator will be based on the number of subjects with a baseline measure and a post-baseline measure of the corresponding time-point.

Change in spleen volume and spleen length

Spleen volume will be measured by MRI/CT at baseline, the end of every 24 weeks (8 cycles for NIS793 arms and 6 cycles for all other arms) and at EOT (if not performed in the past 12 weeks) for Part 1 core treatment phase and extension phase. The change from baseline will be summarized at each scheduled assessment time point by treatment group using descriptive statistics. The change from baseline at the end of Week 24 will be displayed graphically for individual subjects by treatment groups.

The proportion of patients with a spleen volume progression will be summarized using descriptive statistics (N, %) at the end of Week 24 and separately at the end of Week 48 by treatment group.

The proportion of subjects achieving at least 25% and 35% reduction in spleen volume from Baseline to the end of Cycle 8 (NIS793 arms) or Cycle 6 (all other arms) and the end of Cycle 16 (NIS793 arms) or Cycle 12 (all other arms) during the core treatment phase as measured by MRI or by CT will be summarized descriptively.

Spleen length measurement will be conducted by manual palpation. Manual palpation will be performed on days 1 and 15 of cycles 1 to 3, and day 1 of subsequent cycles for Part 1 core treatment phase and extension treatment phase. The change from baseline at each planned

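### Spleen volume progression at Weeks 24 and 48 is counted only from scans inside two 57-day windows, so subjects who progress earlier normally drop out of the numerator

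*SAP*

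**What the plan says.** SAP 2.7.1 analyses all secondary efficacy endpoints in the FAS. For spleen volume progression it says: "The proportion of patients with a spleen volume progression will be summarized using descriptive statistics (N, %) at the end of Week 24". A second summary, for Week 48, follows the same pattern, and both are given per treatment group. The general convention in SAP 2.1 is "Percentages will be calculated using the number of subjects in the relevant population or subgroup as the denominator", with the allowance that "a missing category will be included as applicable".

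SAP 2.1.1 sets the rule for assigning assessments: "In order to summarize data collected over time (including unscheduled visits), the assessments will be time slotted". It applies this to imaging explicitly: "The following time windows are defined for descriptive summary on spleen imaging, spleen length palpation, ePROs, laboratory assessments". In Table 2-1 the Week 24 scan (Cycle 7 Day 1) has a window of Study Days 140–196 and the Week 48 scan (Cycle 13 Day 1) has "Study Days 308 – 364". The table footnote adds: "EOT core and EOT extension assessments are mapped to the corresponding time points based on the defined time window".

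Protocol 12.5.1.2 plans the same summary and says "A spleen progression requires confirmation by MRI or CT showing a spleen volume increase of at least" 25%.

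**The concern.** Progression is not an ordinary repeated measurement, because it stops the measurements that would follow. Protocol 8.3.1.2 calls for imaging without delay when progression is suspected, and 8.3.2.2 sends a subject for MRI/CT when palpation criteria are met. Protocol 9.1.1 makes disease progression a mandatory reason to stop study treatment. The EOT visit follows within 7 days where possible, and its scan is not repeated if one was done in the past 12 weeks (Table 8-2 footnote, Table 8-6). The safety follow-up visits in Table 8-2 have no abdominal imaging.

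A subject with confirmed progression outside the windows has therefore met the protocol's own imaging standard but contributes to neither percentage. No rule in the SAP carries the event forward. The loss is systematic, and the earlier the progression the more likely it is to be lost. With progression-free survival no longer analysed, this is the only planned summary percentage specific to spleen volume progression, and it is the one a reader would quote.

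**Working it through.** **Inputs.** Windows and planned days: SAP Table 2-1. Denominator: SAP 2.7.1 and 2.1. Palpation schedule: Protocol 8.3.2.2. Stopping rule and EOT timing: Protocol 9.1.1. EOT scan waiver: Protocol Tables 8-2 and 8-6. Group size: about 6 per siremadlin cohort (Protocol 6.1.3), with cohorts of 3 to 6 (Protocol 6.5.2).

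**Step 1: reproduce the plan's windows.** Planned day = (cycle − 1) × 28; window = planned day ± 28.
- Cycle 7: 6 × 28 = 168, giving 140–196.
- Cycle 13: 12 × 28 = 336, giving 308–364.

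Both match Table 2-1.

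**Step 2: window coverage in the first year.**
- Each window: 57 days (196 − 140 + 1 and 364 − 308 + 1); together 114.
- Days 2–364: 363 days. Outside both windows: 363 − 114 = 249 (Days 2–139 = 138; Days 197–307 = 111), or 249/363 = 68.6%.
- Up to Day 196, days before the Week 24 window: 138/195 = 70.8%.
- Up to Day 364, days before the Week 48 window: 306/363 = 84.3%.

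These are shares of calendar days, not of events. Scheduled scans fall inside the windows.

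**Step 3: visits that can trigger an on-demand scan.** In the 28-day arms, post-baseline palpation visits up to Cycle 13 Day 1 fall on Days 15, 29, 43, 57, 71, 85 and 113 (before the first window), 141 and 169 (inside it), 197, 225, 253 and 281 (between the windows), and 309 and 337 (inside the second). A confirmatory scan done on any of 11 of these 15 visit days maps to no time point.

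**Step 4: could the EOT scan restore the subject?** Assume treatment stops within 7 days of the confirming scan. With EOT within a further 7 days, the gap is at most 14 days, well under 12 weeks (84 days). No EOT scan is then required. A discretionary scan or delayed stopping could still fall in a window, hence the word normally.

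**Step 5: weight of one event.** 1/6 = 16.7 percentage points; 1/3 = 33.3 in a cohort of 3.

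**Step 6: illustration with assumed counts, n = 6.** One subject progresses at the Week 24 scan. k progress on on-demand scans before Day 140. One non-progressor stops for another reason, last scanned before Day 140. None progress on Days 308–364.

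| k | Week 24 as written | Week 48 as written | Cumulative, both times: (1+k)/6 | Upper bound: (2+k)/6 |
|---|---|---|---|---|
| 0 | 1/6 = 17% | 0/6 | 17% | 33% |
| 1 | 1/6 = 17% | 0/6 | 33% | 50% |
| 2 | 1/6 = 17% | 0/6 | 50% | 67% |

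The windowed figures are the same for every k. The upper bound treats the early-stopped subject as having progressed unseen.

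**The case against.** The strongest reply is that SAP 2.7.1 never defines the numerator for this proportion. For hemoglobin and symptom worsening it requires a measurement at the time point; here it is silent, and the protocol's wording for this summary could be read cumulatively. The SAP also says EOT assessments are mapped as needed. This does not rescue the plan: SAP 2.1.1 applies the windows to descriptive summaries of spleen imaging by name, the Table 2-1 footnote ties EOT mapping to those windows, and nothing carries progression forward. The protocol wording settles neither reading, since Protocol 12.4.4 uses similar words for a change at a visit. No conflict between protocol and SAP is claimed.

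A second reply is that an at-visit proportion is legitimate and may fall between Week 24 and Week 48. That is true of a quantity measured on everyone still followed. Here the event itself removes subjects while the denominator stays at the FAS. A missing row would not solve this, because it would report an observed event as unknown.

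Several points stand. The day shares say nothing about how often off-window progression occurs, and the palpation triggers are demanding. The proportion is descriptive, single-arm and not a named spleen endpoint. All scans are listed (SAP 2.1.1), progression dates and criteria are listed (SAP 2.7.1), and discontinuation reasons are tabulated (SAP 2.3.1), so the information is not lost. Planned core treatment was 24 weeks, so many subjects may lack a Week 48 scan for reasons unrelated to progression. A cumulative count inherits that gap unless it is shown.

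**Conclusion.** The concern holds. As written, the Week 24 and Week 48 proportions count only progression seen on scans in Days 140–196 and 308–364, and earlier progressors normally leave the numerator of a FAS percentage. The direction is towards understating progression. The size is unknown because the documents give no progression rate; each lost event is worth 16.7 points in a group of 6.

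The conclusion assumes that the FAS is the denominator, as SAP 2.7.1 and the general convention imply, and that subjects stop treatment promptly once progression is confirmed. If only subjects with a scan in the window were used instead, early progressors would drop out of both numerator and denominator. The change should be made because it is cheap, but it affects one summary percentage and no decision rule.

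**What to change.** In SAP 2.7.1, count a FAS subject as progressed by Week 24 if any post-baseline MRI/CT up to Study Day 196, whether scheduled, on-demand or EOT, shows a spleen volume at least 25% above baseline. Count as progressed by Week 48 if any such scan occurs up to Study Day 364. Add two rows: (a) subjects with no post-baseline scan, and (b) subjects without progression whose last scan precedes the relevant window. Without row (b) a cumulative count would treat those subjects as fully followed; at Week 48 it may hold much of the group. Keep the Table 2-1 windows for mean change and for the 25% and 35% reductions. Record the definition in SAP section 4.

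The cost is a short definition, two table rows and one entry in section 4, all derived from scans already in the database. The reported proportion may become less favourable. The change would come after enrolment closed in an open-label study and must be documented as such. If the primary CSR tables already exist, which the documents do not say, present the cumulative count as a supplementary table beside the windowed figure.

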2.8 Safety analyses

For all safety analyses, the safety set will be used, except for summaries of DLTs, for which the dose-determining set will be used in addition to the safety set. All listings and tables will be presented by treatment group. Safety summaries (tables, figures) include only data from the on-treatment period with the exception of baseline data which will also be summarized where appropriate (e.g. change from baseline summaries). In addition, a separate summary for death including on treatment and post treatment deaths will be provided. In particular, summary tables for adverse events (AEs) will summarize only on-treatment events, with a start date during the on-treatment period (treatment-emergent AEs).

The overall observation period will be divided into three mutually exclusive segments (pre-, on-, post- treatment period) in addition to overall safety period and on-extension treatment period as defined in [Section 2.1.1](#).

In final CSR, patient safety information related to adverse events from the extension phase will be summarized together with data from phase I core.

2.8.1 Adverse events (AEs)

AE summaries will include all AEs occurring (new or worsening) during the **on treatment period**. In addition, all AEs and SAEs which started during the **overall safety period** will be summarized. AEs collected in the AE (e)CRF page will be listed along with the information collected on those AEs e.g. AE relationship to study drug, AE outcome etc. AEs with start date outside of on-treatment period (pre-treatment period, post-treatment period, and post-treatment overall safety period) will be flagged in the listings.

AEs will be summarized by number and percentage of subjects having at least one AE, having at least one AE in each primary system organ class (SOC) and for each preferred term (PT) using MedDRA coding. A subject with multiple occurrences of an AE will be counted only once in the respective AE category. Grading of AEs is based on NCI Common Terminology Criteria for Adverse Events (CTCAE) version 5.0. A subject with multiple CTCAE grades for the same preferred term will be summarized under the maximum CTCAE grade recorded for the event . AE with missing CTCAE grade will be included in the 'All grades' column of the summary tables.

In AE summaries, the primary system organ class will be presented alphabetically and the preferred terms will be sorted within primary SOC in descending frequency. The sort order for the preferred term will be based on their frequency in the total column.

The following adverse event summaries will be produced by treatment arm; overview of adverse events and deaths (number and % of subjects who died, with any AE, any SAE, any dose reductions/interruptions, leading to treatment discontinuation, requiring additional therapy), AEs by SOC and PT, summarized by relationship (all AEs and AEs related to study treatment), seriousness (SAEs and non-SAEs), leading to treatment discontinuation, leading to dose interruption/adjustment, requiring additional therapy and leading to fatal outcome. In addition, a summary of serious adverse events with number of occurrences will be produced (an occurrence is defined as >1 day between start and prior end date of record of same preferred term).

As recommended in the COVID-19 (Coronavirus) Guidance for Clinical Trial Teams - *Developing Clinical Study Reports (CSRs) for Studies Conducted During the COVID-19 Pandemic*, all suspected or confirmed SARS-CoV-2 infections will be listed for all patients and by treatment groups. The infected cases will be selected using specified criteria as detailed in the TFL shells document.

2.8.1.1 Adverse events of special interest / grouping of AEs

Adverse events of special interest (AESI) during the on-treatment period will be tabulated. The list of AESI will also include relevant events for ruxolitinib, and the novel agents including but not limited to sitemartin, crizanlizumab, sabatolimab and NIS793, if deemed appropriate.

Data analysis of AESIs

An adverse event of special interest is a grouping of adverse events that are of scientific and medical concern specific to compound ruxolitinib and the individual novel agents, if deemed appropriate. These groupings are defined using MedDRA terms, SMQs (standardized MedDRA queries), HGLTs (high level group terms), HLT (high level terms) and PTs (preferred terms). Customized SMQs (Novartis MedDRA queries, NMQ) may also be used. A NMQ is a customized group of search terms which defines a medical concept for which there is no official SMQ available or the available SMQ does not completely fit the need. It may include a combination of single terms and/or an existing SMQ, narrow or broad. All AESI terms for the individual compounds as well as for combination specific AESIs, if deemed appropriate, are captured in the case retrieval strategy/strategies (CRS).

For each specified AESI, number and percentage of patients with at least one event of the AESI occurring during on treatment period will be summarized. Summaries of these AESIs will be provided by treatment arm, (specifying grade, SAE, relationship, action taken, medication or therapy taken, AE outcome). A listing of all grouping levels down to the MedDRA preferred terms used to define each AESI will be generated.

